CIPN relates to the cumulative doses of chemotherapeutic agents. Sometimes, when chemotherapy is stopped, neuropathy symptoms may continue or worsen, which is called a "costing phenomenon." Nerve damaging usually starts from the ends of the extremities; while individual doses were accumulated, it gradually extends to proximal joints or ganglions. CIPN is currently the second most common side, next to hematotoxicity. Within thirty days after chemotherapy, 68.1% of patients may develop CIPN, most of which can be relieved or improved, but there are still 30-83% symptoms persist over 6 months[1].

At present, the most effective way to treat CIPN is to stop the treatment protocol or adjust doses of chemotherapy; however, it affects the effect of chemotherapy in degrading tumor growth. Plenty of pharmacological or non-pharmacological treatments are still under investigation, such as antioxidant medication (e.g. Acetyl-L-carnitine, glutamine, vit B₁₂, fish oil, etc.), anxiolytics (e.g. venlafaxine), neuroprotective agents (e.g. infusion of calcium ions, magnesium ions), food supplements, acupuncture, light stimulation, etc. Acupuncture with the advantages of clinically effective, easy-practice and relatively safe, few studies revealed its effect on CIPN. However, there is still a lack of large clinical trials to evaluate its effectiveness[1].

(ii) Purpose of the research

To investigate the efficacy of acupuncture on peripheral neuropathy after chemotherapy administration in patients with breast cancer.

(iii) Importance of the research

Current studies revealed that acupuncture might be useful on CIPN; however, an insufficient number of participants or lack of control groups limit the quality of clinical studies. Therefore, the aim of our study to conduct a randomized controlled clinical trial to evaluate the efficacy of acupuncture on peripheral neuropathy caused by chemotherapy.

(iv) Domestic and international researches on this plan

In 2013, Giovanna Franconi et al. published a systematic review that screened the database of MEDLINE, Google Scholar, Cochrane Database, CINHAL, CNKI, Wanfang Med Online, ISI Proceedings. The screened year was set before 2012, and 3989 journal articles were screened. With excluding acupuncture irrelevant or duplicate articles, or researches unrelated to neuropathy and

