This randomized controlled clinical trial explores the efficacy of combined acupuncture and drug treatment (conventional cancer therapy) in women with breast cancer after chemotherapy causes peripheral neuropathy. The study adopted convenience sampling and randomized allocation, all the participants were screened from the patients with breast cancer who visited the Department of Traditional Chinese Medicine at Tainan Municipal An-Nan Hospital-China Medical University, Tainan, Taiwan.

The inclusion criteria will be: female more than 20 years of age; breast cancer with early-stage at I-III; had completed chemotherapy; the neurotoxic chemotherapeutic agents included taxanes, platinums, or others; less than grade three in the Eastern Cooperative Oncology Group (ECOG) status; higher than grade one in National Cancer Institute-common terminology criteria for adverse events(NCI-CTCAE) scale.

The exclusion criteria will be: having less than three months in mean survival time, history of diabetic neuropathy before chemotherapy administration, history of other preexisting peripheral neuropathy, other inflammatory or metabolic arthritis, severe blood coagulation diseases or with latent bleeding tendency, unstable cardiovascular diseases, or other preexisting muscle-skeletal diseases.

Figure 1 showed the flow chart of the research:

[figure not shown]

Figure 1. The flow chart of the study

The evaluation tools used in the research are:

- (1) Brief Pain Inventory-short form: To assess the location of pain and the level of pain. Items are scored from 0 to 10 (0= no pain; 10= pain as bad as you can imagine) to evaluate the degree of pain and the impact of pain on daily life.
- (2) FACT/GOG-NTX-13: To evaluate the changes in peripheral neuropathy such as sensory, motor, touch, cold and heat sensations, and the impact of pain on daily life. Items are scored from 0-4 (0 = not at all; 4 = very much) and summed.
- (3) WHOQOL-BREF (Taiwan version): To evaluate the degree of improvement in the quality of life after receiving acupuncture treatment. Items are scored from 1-5 (1 =being very dissatisfied, 2 =dissatisfied, 3 =No comments, 4 =satisfaction, 5 =very satisfied).
- (4) Touch Test Sensory Evaluator: Use 20 von Frey monofilaments to test the degree of the tactile sensation of the patient's fingertips, tips of the toe, palms, and planters.

The treatment protocol will be designed as:

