- (1) The acupuncture group: Acupuncture treatment will be performed for 9 weeks. The frequency of acupuncture will be twice a week for the first six weeks, and once a week for the following three weeks. 30 minutes needling at each treatment. Acupuncture points include Baihui(GV20), Qihai(CV6), Quchi(LI11), Hegu(LI4), Neiguan(P6), or Shenmen(HT7) for upper limbs. For plantar numbness, choose two acupoints to use in turn; use Weizhong(BL40), Sanyinjiao(SP6), or Zusanli(ST36) for lower limbs. If severe numbness occurred, Taixi(KI3) or Yongquan(K1) should be added for feet numbness. “De qi” sensation, such as soreness, numbness, pain, etc. will be achieved at each acupoints .

(2) The controlled group: Acupuncture with minimal needling 0.5 *cun* (estimated 1cm with deviation depends on the body size of each participant) away from the acupoints, which only superficially penetrated the skin without the feeling of “De Qi” sensation.

The conventional cancer treatment for CIPN was the same in the two groups.

Within nine weeks of treatments, questionnaires were assessed before treatment, at week three, week six, and week nine to follow-up the changes of peripheral neuropathy on each participant.

Explore the neuroprotective mechanism of acupuncture: 15 cc of blood samples will be drawn before and after 15 sessions of treatments from participants in both groups. The blood samples will be analyzed by enzyme-linked immunosorbent assay (ELISA) for tumor necrosis factor-alfa and interleukin- 6, interleukin-10 and brain-derived nuerotrophic factor to evaluate the differences in the inflammation state of the peripheral nervous system within and between groups.

Statistical analysis:

This is a two-group, parallel controlled clinical trial; the null hypothesis will be no significant difference in BPI-SF between the two groups. The estimated standard deviation was 2, the power was set to 94%, a two-tail test, $\alpha=0.05$, and the estimated number of patients was at least 25 in each group.

A two-sample t-test will be used to compare the difference between the treatment group and the controlled group.

A Paired-t-test will be used to compare the changes in the assessment scale at week 3, week 6 and week 12.

One way ANOVA: Analyze the relationship between the demographic data of subjects, breast cancer grade and other category variables and the evaluation scale.

(ii) Expected difficulties and solutions

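### The only stated test of change over time is a paired t-test with no defined role; efficacy should rest on the between-arm difference in change

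*Combined protocol and SAP*

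**What the plan says.** The statistical analysis part of section D(i) names three methods and does not rank them.

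- For the comparison of arms: "A two-sample t-test will be used to compare the difference between the treatment group and the controlled group". Neither the outcome nor the visit is named, and the text does not say whether the variable is a score or a change.
- For change over time: "A Paired-t-test will be used to compare the changes in the assessment scale", with weeks 3, 6 and 12 named. No arm, reference visit or role is given. A paired test of one scale across visits can hardly be anything but a within-patient comparison, so within-arm change from baseline is the natural reading, though an inferred one.
- A one-way ANOVA relates patient characteristics to the scales.

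The hypothesis is between arms: "the null hypothesis will be no significant difference in BPI-SF between the two groups". No hypothesis is given for FACT/GOG-NTX-13, WHOQOL-BREF or the monofilament test.

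Two other places use before-after language. The purpose of WHOQOL-BREF is "To evaluate the degree of improvement in the quality of life after receiving acupuncture treatment". The ELISA markers are drawn before and after 15 sessions "to evaluate the differences in the inflammation state of the peripheral nervous system within and between groups".

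On natural course, the background in C(i) says of chemotherapy-induced neuropathy: "most of which can be relieved or improved, but there are still 30-83% symptoms persist over 6 months". It adds that symptoms can persist or get worse once chemotherapy stops. Patients enter after finishing chemotherapy, with no window since the last dose and a CTCAE grade above one. Conventional treatment for neuropathy is the same in both arms.

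**The concern.** Change from baseline inside one arm is the sum of several things: any effect of needling at the acupoints, the natural course after chemotherapy, regression to the mean after selection on symptom grade, non-specific response to being treated, and the conventional treatment. A paired t-test asks only whether that sum is zero. Randomisation against the minimal-needling control removes the shared parts, but only when the arms are compared with each other.

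The opening summary aims to establish that acupuncture improves neuropathy and, through it, quality of life. Because the between-arm hypothesis covers BPI-SF alone and the paired test has no assigned role, nothing stops a significant within-arm result on another scale or marker from being used to support that aim, even if the arms do not differ. The same applies to the pattern of significance in the acupuncture arm but not in the control arm, which is not a test of the difference between them.

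**Working it through.** **1. The plan's own figure.** Inputs from D(i): SD 2, power 94%, two-sided α 0.05, at least 25 per group. The difference to be detected is not stated. With an assumed difference of 2 points:

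n per group = 2 × SD² × (1.960 + 1.555)² / difference² = 2 × 4 × 12.35 / 4 = 24.7, rounded up to 25.

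Power at n = 25 is 94.2% by the normal approximation and 93.4% by the noncentral t. The stated size therefore fits a two-sample comparison with an unstated difference of about 2 points, in line with the between-arm null.

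**2. Assumptions for the illustration.** The documents do not give these.
- Acupuncture has no effect, and both arms improve by the same mean amount m on BPI-SF.
- There are 25 patients per arm.
- The SD of change is 2. The plan says "The estimated standard deviation was 2" without saying whether it belongs to the score or to the change. If it is the SD of the score at both visits, SD of change = 2 × √(2(1 − r)), where r is the correlation between visits. This gives 2.83 at r = 0, 2.0 at r = 0.5 and 1.5 at r ≈ 0.72.

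**3. Paired test in one arm.** The statistic follows a noncentral t with 24 degrees of freedom and noncentrality m / (SD of change / √25). With SD of change 2, noncentrality = m / 0.4.

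| m (points) | Noncentrality | P(significant, two-sided 0.05) |
|---|---|---|
| 0 | 0 | 5% |
| 0.5 | 1.25 | 23% |
| 1.0 | 2.5 | 67% |
| 1.5 | 3.75 | 95% |

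At m = 1.0 the probability is 40% with SD of change 2.83 and 89% with 1.5.

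**4. Between-arm test of change on the same data.** The shared m cancels in the difference of arm means, so the rejection rate does not depend on m. Simulation of 100,000 trials (SD of change 2) gave 4.9%, 4.9%, 4.9% and 5.0% for m = 0, 0.5, 1 and 2.

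**5. Separate paired tests compared by eye.** At m = 1.0 and SD of change 2, each arm shows significant improvement with probability 0.670, independently. Exactly one arm does so with probability 2 × 0.670 × 0.330 = 0.442. In half of these, 0.670 × 0.330 = 0.221 of all trials, it is the acupuncture arm alone. For exactly one arm, the figure is 19% with SD of change 1.5 and 48% with 2.83.

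**The case against.** The strongest reply is that the trial already has the right comparison. The only hypothesis is between randomised arms, a two-sample test is listed first, the control is needled too, and conventional treatment is the same, so shared recovery cancels. Reporting within-group change beside a randomised comparison is common and not invalid in itself. All of this stands.

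A reader might go further and infer that natural recovery will be counted as an acupuncture effect. The documents do not support that: no section says how a paired result will be interpreted. A reader might also infer that the background describes spontaneous recovery. It does not say that the improvement is spontaneous, and it reports persistence and worsening as well. Neither the direction nor the size of drift over these nine weeks is established.

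Nor are the percentages false-positive rates of the paired test as such. If the mean truly changes by 1 point, the paired null is false and rejecting it is correct. The error arises only when the change is attributed to acupuncture. The calculation covers one BPI-SF test and says nothing about how many scales would be significant.

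Two of the supporting lines are modest evidence. The WHOQOL-BREF sentence describes an instrument and is not an analysis rule. The ELISA sentence also provides for a between-group comparison.

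The gap remains. The between-arm hypothesis does not reach beyond BPI-SF, the paired test is the only one tied to change over the visits, and the plan neither assigns it a role nor rules out a causal reading.

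**Conclusion.** The point holds in this limited form: the role of the paired t-test is undefined, and within-arm significance on the scales or markers cannot support the trial's aim. It is a should-fix, a cheap improvement. The between-arm BPI-SF comparison and its sample size are not affected.

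The illustrated size (23% to 95% for one paired test, against about 5% for the between-arm test) rests on an assumed shared improvement of 0.5 to 1.5 points, an assumed SD of change of 2 and no acupuncture effect. With no drift the paired test is also at 5%. With average worsening the bias would run the other way and could hide a benefit. The conclusion about method does not depend on these values, since a within-arm test cannot separate treatment from drift in either direction. The mismatch between the week 12 named for the paired test and assessments that end at week 9 is a separate matter, and correcting it would leave this one in place.

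**What to change.** In the statistical analysis part of D(i):

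- For every scale, test the between-arm difference in change from baseline at each scheduled visit (weeks 3, 6 and 9), for example by ANCOVA adjusted for the baseline value. For the ELISA markers, do the same at the draw after the 15 sessions.
- State that all conclusions about efficacy and mechanism rest on these between-arm differences.
- Keep within-arm changes as description only: mean change with 95% confidence interval and no efficacy claim. Say explicitly that significance in one arm but not the other will not be read as a difference between arms.
- Reword the WHOQOL-BREF purpose as the between-arm difference in change.

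Several scales and visits mean several between-arm tests, so the text should keep the BPI-SF comparison, on which the sample size rests, distinct from the others. The change needs no extra patients, visits or data. The price is that fewer within-arm significant results can be claimed.
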